10.0 EXTENT OF EXPOSURE TO STUDY DRUG

Each subject will receive a single IV injection of BMN 270, and the volume of infusion will depend on the dose level and subject weight. Study drug dosing compliance will be assessed by providing descriptive summaries of actual dose, and number of administered study drug infusions below the planned dose. The follow-up time of each subject will be summarized descriptively.

A data listing of drug exposure will be provided.

11.0 EFFICACY EVALUATIONS

This section describes the analyses to be undertaken for the primary, secondary, and other efficacy variables. Efficacy at week 16 after BMN 270 infusion will be analyzed. Long-term efficacy based on data including but not exclusive to week 26, week 52, and up to 5 years post-BMN 270 dosing will be evaluated.

As it is expected to take four weeks for the endogenous production of FVIII following gene transfer to be efficacious, for the purpose of data review and interpretation, the efficacy period will be defined as

Proprietary and Confidential Pg. 15 of 38

starting from week 5 post-BMN 270 dosing until subjects resume routine FVIII prophylaxis, should that occur before the end of the safety long term follow up or ETV, whichever is earlier.

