11.2 Secondary Efficacy Endpoint(s)

The secondary efficacy endpoints are:

Annualized bleeding rate (ABR) (counts/yr.)

 $= \frac{\text{Number of bleeding episodes during calculation period}}{\text{Total number of days during the calculation period}} \times 365.25$

Annualized FVIII use (IU/kg/yr.)

 $= \frac{\text{Sum of FVIII use(IU/kg) during calculation period}}{\text{Total number of days during the calculation period}} \times 365.25$

Annualized FVIII infusion rate (count/yr.)

Proprietary and Confidential Pg. 17 of 38

= Number of FVIII replacement infusions during calculation period

Total number of days during the calculation period

Subjects will be asked at each study visit to report the number of bleeding episodes and the use of factor replacement therapy since the previous visit. This information will be captured on the subject's diary or other subject records. A bleeding episode is defined as a bleed or symptoms associated with the development of a bleed (or multiple bleeds occurred in the same day) requiring FVIII replacement treatment.

The calculation period in the above formulas for post-baseline values will be Weeks 1-4, Weeks 5-26, Weeks 5-52, and Weeks 5 and beyond.

The baseline values for the secondary endpoints will be based on the historical data prior to study enrollment.

The ABR by individual subject and ABR descriptive statistics over time (pre-infusion and post-infusion calculation periods) by cohort will be tabulated. Such tabulation may also be performed for subgroups defined by baseline FVIII treatment regimen (on-demand vs. prophylaxis). The same tabulation will be performed for ABR before FVIII activity achieving 5 IU/dL and ABR after FVIII activity achieving 5 IU/dL. The ABR change from pre-infusion will be summarized by cohort. Summaries by the bleeding site (target joint, non-target joint), bleeding cause (spontaneous, traumatic), by cohort may also be performed for ABR. Scatter plots of post-infusion individual bleeding episodes over time will be plotted. A comparison of pre-infusion and post-infusion ABR using Poisson regression model followed by a test for overdispersion will be performed. The ABR will be analyzed using negative binomial regression if overdispersion exists. A comparison using a Wilcoxon signed-rank test may also be performed.

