The above ABR analyses will be repeated for treated bleeds, as defined using standard criteria defined by the Subcommittee on Standards and Criteria, FVIII/FIX subcommittee of the International Society of Thrombosis and Hemostasis. A bleed is considered to be a "treated bleed" if it is directly followed by a haemophilia medication reported to be a "treatment for bleeding episode" irrespective of the time between the treatment and the preceding bleed (i.e., there is not an intervening bleed). A bleed and the first treatment thereafter are considered to be pairs (i.e., one treatment belongs to one bleed only), with the following exception: if multiple bleeds occur on the same calendar day, the subsequent treatment is considered to apply for each of these multiple bleeds (which are, however, counted as separate treated bleeds). Bleeds due to surgery/procedure are not included in the primary analysis. Only treatments that were recorded as "treatment for bleeding episode" are included in the determination of a treated bleed. Two bleeds at the same anatomical location are considered to be one bleed if the second occurs within 72 hours from the last treatment for the first bleed. The last treatment is defined as the last treatment before a new bleed occurs, either in the same or in a different location. This is in line with the above definition that bleeds and treatments are considered to be pairs.

The Annualized FVIII use and Annualized FVIII infusion rate will be analyzed similarly as ABR. The post-infusion and pre-infusion annualized FVIII use will be compared using a paired t-test. The FVIII replacement treatment by the following different categories will also be summarized:

- Treatment for adverse events (including all bleeds, and symptoms associated with the development of a bleed or bruises that would occur in a non-haemophiliac person per protocol)
- Treatment for bleeding episode (including all bleeds, and symptoms associated with the
 development of a bleed or bruises that are normal events of haemophilia but should not be
 treated as AEs per protocol)
- Prophylaxis (routine)
- Surgery/procedure
- Prophylaxis (precautionary due to activity/injury)

The analyses described for the secondary endpoints will be conducted for the FAS analysis population. Sensitivity analyses using PP analysis population may be performed for secondary endpoints, if applicable.

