11.2.1 Correlation between FVIII Activity and Bleeding Risk

FVIII activity is widely acknowledged to be a key aspect of hemophilia A and a valuable indicator of patients' status, while annualized bleeding rate has been traditionally used as the primary clinical endpoint for replacement therapy. The correlation between FVIII activity level and bleeding risk has been researched, showing that increases in FVIII activity levels are predictably associated with a decreased number of annual bleeds (Den Uijl, 2011, Haemophilia). The following analyses will be performed to explore the relationship between measured FVIII activity and bleeding in this study.

- Based on the FVIII activity visit windows (Appendix 1), median FVIII activity and total number of treated bleeds (defined in Section 11.2) will be calculated for each window for every subject. A negative binomial regression will be performed, modelling number of bleeds in each window vs. FVIII activity in the window. The analysis will be done for FVIII activity measured by one-stage clotting assay and chromogenic assay separately. The same analyses will be conducted for treated joint bleeds. The analysis will use observed cases and be performed for the Full Analysis Set.
- Using a cutoff of FVIII activity level, e.g., 40 IU/dL, each subject's data will be divided into 2 periods: from Week 5 to the first time reaching 40 IU/dL, and from the first time reaching 40 IU/dL to the end of efficacy period. For each period, the duration of the period, the number of bleeds, the ABR, and the change in ABR from baseline will be listed and summarized. The analysis will be performed using various cutoffs, such as 5, 15, 25, 30, 40 IU/dL.

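### The bleed and FVIII-use endpoints have no consistent rule for a subject who starts routine prophylaxis, above all with a non-FVIII product, so that time can be credited to BMN 270

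*SAP*

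**What the plan says.** Section 11.0 starts the efficacy period at week 5. It closes the period early only when routine FVIII prophylaxis resumes ("until subjects resume routine FVIII prophylaxis"); otherwise it runs to the end of long-term follow-up or early termination. The stated purpose is limited: "for the purpose of data review and interpretation, the efficacy period will be defined as" and so on. The end of this period is named again in only one analysis, the FVIII-cutoff split in section 11.2.1, which runs "to the end of efficacy period".

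Section 11.2 defines a bleeding episode as one "requiring FVIII replacement treatment". The use endpoint takes the "Sum of FVIII use(IU/kg) during calculation period" and the infusion endpoint the "Number of FVIII replacement infusions during calculation period". All three are tied to FVIII. The ABR analyses are then repeated for treated bleeds, where a bleed qualifies if it is "directly followed by a haemophilia medication reported to be a" treatment for a bleeding episode. That wording names no product.

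The post-infusion calculation periods for ABR and use are Weeks 1-4, Weeks 5-26, Weeks 5-52, and Weeks 5 and beyond. Appendix 17.1 gives the last as Day 33 onward with no upper limit. None of them refers to the efficacy period.

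**The concern.** Four rules that should work together use different product scopes or different stopping points. The SAP has no rule that ends, censors or flags bleed and use data when a subject starts routine haemophilia prophylaxis with something other than FVIII. For the listed ABR and use periods, it has no such rule for FVIII prophylaxis either.

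Two results are at stake. First, bleed control achieved by another product would be annualised as if BMN 270 had produced it. This feeds the pre/post ABR comparison (Poisson or negative binomial regression, possibly Wilcoxon) and the paired t-test on annualized FVIII use. Second, a bleed treated with a non-FVIII product could count as a treated bleed without being a bleeding episode, so the main and repeat ABR could disagree about the same event.

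**Working it through.** The SAP states no figure on this point, and no power or sample-size calculation, so there is nothing to reproduce. The check compares the rules and then applies the SAP's own rate formula.

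**Which rule responds to which event**

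| Rule | Routine FVIII prophylaxis starts | Routine non-FVIII prophylaxis starts |
|---|---|---|
| Efficacy period (11.0; used in the 11.2.1 cutoff split) | Ends | Stays open |
| ABR, Weeks 5 and beyond (11.2, Appendix 17.1) | No stop | No stop |
| FVIII use and infusion rate, same period | No stop, but the FVIII is counted | No stop, and prophylaxis adds zero |

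For a bleed treated with a non-FVIII product, the main definition does not count it. The treated-bleed definition, read literally, does.

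The gap therefore exists whichever period is taken to govern ABR. If the efficacy period governs, its trigger misses non-FVIII prophylaxis. If the listed periods govern, no prophylaxis stops them, though resumed FVIII would at least show in the use endpoints.

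**Effect on the Weeks 5 and beyond rate**

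Inputs from Appendix 17.1: start Day 33; Week 260 at Day 1821. Total days = 1821 − 33 + 1 = 1789. For prophylaxis starting on day S, the days before it are S − 33. With events/days × 365.25 from section 11.2,

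reported rate = [pre-switch rate × (S − 33) + post-switch rate × (1789 − (S − 33))] / 1789.

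The switch days and bleed rates below are assumptions; the SAP gives neither.

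| Assumed switch | S | Days before | Days after | Share after | Reported ÷ pre-switch rate, no counted events after | ABR reported: 5 before, 0 after | ABR reported: 5 before, 1 after |
|---|---|---|---|---|---|---|---|
| Week 52 | 365 | 332 | 1457 | 81% | 0.19 | 0.93 | 1.74 |
| Week 104 | 729 | 696 | 1093 | 61% | 0.39 | 1.95 | 2.56 |
| Week 156 | 1093 | 1060 | 729 | 41% | 0.59 | 2.96 | 3.37 |
| Week 208 | 1457 | 1424 | 365 | 20% | 0.80 | 3.98 | 4.18 |

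Example: 5 × 696 / 1789 = 1.95. If the period ended at the switch, the ABR would stay at 5. The same factors apply to annualized FVIII use: an assumed 1000 IU/kg/yr before a Week 104 switch is reported as 1000 × 696 / 1789 = 389.

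One subject carries weight in cohorts of this size. Cohort 4 is 3 subjects, possibly 6 (section 2.2), so one subject is 1/3 = 33% or 1/6 = 17% of it.

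**The case against.** The strongest reply is that the treated-bleed wording is generic. The SAP takes it from an international subcommittee covering both FVIII and FIX. It counts only treatments recorded as given for a bleeding episode, and section 11.2 then lists that label among the categories of FVIII replacement ("The FVIII replacement treatment by the following different categories will also be summarized"). On that reading the medication is FVIII and the two bleed definitions agree on product. This is a fair reading, but the text does not settle it. Even if it is accepted, the missing rule for routine prophylaxis remains.

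A second reply is that the use endpoints match their objective, which concerns FVIII replacement, and that other medicines would appear in the concomitant-medication summary (section 9.0). Both are true. That summary does not adjust efficacy time, however, and the treatment categories in section 11.2 have no place for non-FVIII prophylaxis.

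Several stronger inferences are tempting and are not supported:

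- **That a switched subject is scored as a lasting BMN 270 success.** Responder status rests only on median FVIII activity in weeks 13-16 (section 11.1), and FVIII activity is followed over time in summaries and plots. None of these uses bleeds or FVIII use. The SAP does not say whether a non-FVIII product would affect the assays.
- **That the treated-bleed rule helps create the problem.** Read broadly, it would still count bleeds treated with another product, so it guards against undercounting.
- **That the 11.2.1 regression would show sustained efficacy.** It models treated bleeds against FVIII activity. Few bleeds at low activity would weaken that relationship.
- **That correcting section 11.0 is enough.** The listed ABR and use periods are not tied to the efficacy period, so that edit alone clearly changes only the 11.2.1 cutoff split.
- **That a subject with an inhibitor would go unseen.** Inhibitor development is an event of interest with a subject listing (section 12.1.5).

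**Conclusion.** The point holds as an inconsistency and a gap in the secondary bleed and use endpoints, and it should be corrected. Under the rules as written, time after the start of routine prophylaxis counts towards BMN 270 in the ABR. With a non-FVIII product, it also counts as zero-use time in FVIII use and infusion rate.

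With a switch assumed between Week 52 and Week 208, follow-up to Day 1821 and no counted events afterwards, the Weeks 5 and beyond rate is about 0.19 to 0.80 of the pre-switch rate. Counted events after the switch make the distortion smaller. The size is illustrative: the SAP does not say that a non-FVIII product is used or allowed, nor how many subjects might switch. The primary endpoints and the longitudinal FVIII activity summaries do not draw on bleeds or FVIII use.

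**What to change.** These changes concern analysis wording only; they set no rule for treatment.

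1. In section 11.2, apply one product rule, any haemophilia medication, to both the bleeding-episode and treated-bleed definitions.
2. In section 11.0, end the efficacy period at the start of any routine haemophilia prophylaxis, FVIII or other.
3. In section 11.2 and Appendix 17.1, end the Weeks 5-26, Weeks 5-52, and Weeks 5 and beyond periods for ABR and use at the end of the efficacy period. Tabulate later time separately instead of including it as zero-use time.
4. In section 11.2.1, exclude or flag windows after that point in the regression. The cutoff split follows from item 2.

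The cost is a SAP revision and some reprogramming. Section 12.1 already has all bleeds recorded whether or not FVIII is needed, and section 9.0 already has all medications coded. The downside is shorter follow-up in the main bleed and use summaries for subjects who switch; the separate tabulation keeps the later time visible.

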11.1 Primary Efficacy Endpoint(s)

Plasma FVIII activity will be determined by validated assays, one-stage clotting and chromogenic substrate assays, assessed by the central lab. Plasma FVIII activity will be assessed weekly for 36 weeks after BMN 270 infusion and continue to have the regularly scheduled assessments as planned in the protocol. The true steady-state of plasma FVIII activity level produced from BMN 270 can only be assessed after a minimum of 72 hours has elapsed since the last infusion of FVIII protein concentrates. Therefore, FVIII activity levels within 72-hours after FVIII use will be excluded from analysis. FVIII activity levels below the LLOQ (Lower limit of quantitation) will be imputed with 0 IU/dL. If FVIII activity level is retested, the retest assessment will be used for all analyses. A listing of original test assessment and retest assessment will be provided.

The primary efficacy endpoints will be:

- Responder/nonresponder status, where a responder is defined as a subject with median FVIII activity of ≥ 5 IU/dL during week 13-16 post-BMN 270 infusion
- Median FVIII activity during week 13-16

11.1.1 Primary Analysis Method

The number and percentage of subjects with median FVIII activity ≥ 5 IU/dL during week 13-16 will be summarized for each dose cohort.

Median FVIII activity during week 13-16 will be summarized descriptively by dose cohort.

Median FVIII activity over time will be summarized descriptively by dose cohort every 4 weeks up to week 104 and every 6 weeks afterwards. The visits and visit windows are defined in Appendix 17.1. Each subject's FVIII activity level in a visit window is defined as the median of the values obtained during the window. Corresponding boxplots of median FVIII activity levels at every 4-week or 6-week interval over time will be provided by cohort.

Individual subject plasma FVIII activity assessments will be presented in plots and listings:

- A bar plot of individual subject median FVIII activity during week 13-16 will be created.
- Individual subject profile plots of FVIII activity assessments over time together with other key
 efficacy and safety endpoints, including bleeding episodes and corresponding exogenous FVIII
 use, ALT assessments, glucocorticoid treatment, and prophylactic glucocorticoid treatment will
 also be presented.
- Line plots ("spaghetti plots") of subject FVIII activity assessments versus study day will be provided by cohort.

The primary analyses will be conducted for both the one-stage clotting and chromogenic substrate assays for the FAS analysis population. The above analyses will be conducted for long-term efficacy data if

Proprietary and Confidential Pg. 16 of 38

needed, e.g., similar analyses may be performed at week 26, week 52, and up to 5 years-post BMN 270 dosing.

11.1.2 Supportive Analysis Methods

The distribution of median FVIII activity level during week 13-16 will be further explored with cumulative distribution function (CDF) plots: the horizontal axis represents the continuum of values of plasma FVIII activity (IU/dL), and the vertical axis shows the percentage of subjects achieving at least that level of activity. Thus, a CDF plot shows the percentage of subjects achieving each level of response. Applying different thresholds along the CDF curve allows interpretation of the curve at various levels of response. Thresholds of particular interest include 5, 15, 25, 30 and 40 IU/dL. The summary of corresponding responder analyses will also be provided.

The distribution of time from infusion to FVIII activity level first achieving 5 IU/dL and the duration of maintaining FVIII activity between levels of 5-150 IU/dL (excluding the time periods when FVIII activity level drops below 5 IU/dL or increases above 150 IU/dL) until Week 16 will also be explored by cohort. The distribution of duration of FVIII activity remaining under 1 IU/dL, between 1-5 IU/dL and above 150 IU/dL may be explored by cohort, if needed.

The intra-subject and inter-subject variability in FVIII activity before and/or after subjects reach steady state may be explored using descriptive statistics and model-based methods.

The supportive analyses will be conducted for the FAS analysis population. The same analyses will be conducted for long-term efficacy data if needed.

11.1.3 Sensitivity Analysis Methods

The analyses described above may be repeated for the PP analysis population if applicable.

To investigate the robustness of the primary analysis, which uses the median FVIII activity value if more than one assessments falls within an analysis window, a sensitivity analysis may be performed using the mean of the multiple assessments.

To investigate the relationship between the FVIII activities by one-stage clotting and chromogenic substrate assays, a regression analysis to fit both assays to a regression line will be conducted.

11.2 Secondary Efficacy Endpoint(s)

The secondary efficacy endpoints are:

Annualized bleeding rate (ABR) (counts/yr.)

 $= \frac{\text{Number of bleeding episodes during calculation period}}{\text{Total number of days during the calculation period}} \times 365.25$

Annualized FVIII use (IU/kg/yr.)

 $= \frac{\text{Sum of FVIII use(IU/kg) during calculation period}}{\text{Total number of days during the calculation period}} \times 365.25$

Annualized FVIII infusion rate (count/yr.)

Proprietary and Confidential Pg. 17 of 38

= Number of FVIII replacement infusions during calculation period

Total number of days during the calculation period

Subjects will be asked at each study visit to report the number of bleeding episodes and the use of factor replacement therapy since the previous visit. This information will be captured on the subject's diary or other subject records. A bleeding episode is defined as a bleed or symptoms associated with the development of a bleed (or multiple bleeds occurred in the same day) requiring FVIII replacement treatment.

The calculation period in the above formulas for post-baseline values will be Weeks 1-4, Weeks 5-26, Weeks 5-52, and Weeks 5 and beyond.

The baseline values for the secondary endpoints will be based on the historical data prior to study enrollment.

The ABR by individual subject and ABR descriptive statistics over time (pre-infusion and post-infusion calculation periods) by cohort will be tabulated. Such tabulation may also be performed for subgroups defined by baseline FVIII treatment regimen (on-demand vs. prophylaxis). The same tabulation will be performed for ABR before FVIII activity achieving 5 IU/dL and ABR after FVIII activity achieving 5 IU/dL. The ABR change from pre-infusion will be summarized by cohort. Summaries by the bleeding site (target joint, non-target joint), bleeding cause (spontaneous, traumatic), by cohort may also be performed for ABR. Scatter plots of post-infusion individual bleeding episodes over time will be plotted. A comparison of pre-infusion and post-infusion ABR using Poisson regression model followed by a test for overdispersion will be performed. The ABR will be analyzed using negative binomial regression if overdispersion exists. A comparison using a Wilcoxon signed-rank test may also be performed.

The above ABR analyses will be repeated for treated bleeds, as defined using standard criteria defined by the Subcommittee on Standards and Criteria, FVIII/FIX subcommittee of the International Society of Thrombosis and Hemostasis. A bleed is considered to be a "treated bleed" if it is directly followed by a haemophilia medication reported to be a "treatment for bleeding episode" irrespective of the time between the treatment and the preceding bleed (i.e., there is not an intervening bleed). A bleed and the first treatment thereafter are considered to be pairs (i.e., one treatment belongs to one bleed only), with the following exception: if multiple bleeds occur on the same calendar day, the subsequent treatment is considered to apply for each of these multiple bleeds (which are, however, counted as separate treated bleeds). Bleeds due to surgery/procedure are not included in the primary analysis. Only treatments that were recorded as "treatment for bleeding episode" are included in the determination of a treated bleed. Two bleeds at the same anatomical location are considered to be one bleed if the second occurs within 72 hours from the last treatment for the first bleed. The last treatment is defined as the last treatment before a new bleed occurs, either in the same or in a different location. This is in line with the above definition that bleeds and treatments are considered to be pairs.

The Annualized FVIII use and Annualized FVIII infusion rate will be analyzed similarly as ABR. The post-infusion and pre-infusion annualized FVIII use will be compared using a paired t-test. The FVIII replacement treatment by the following different categories will also be summarized:

- Treatment for adverse events (including all bleeds, and symptoms associated with the development of a bleed or bruises that would occur in a non-haemophiliac person per protocol)
- Treatment for bleeding episode (including all bleeds, and symptoms associated with the
 development of a bleed or bruises that are normal events of haemophilia but should not be
 treated as AEs per protocol)
- Prophylaxis (routine)
- Surgery/procedure
- Prophylaxis (precautionary due to activity/injury)

The analyses described for the secondary endpoints will be conducted for the FAS analysis population. Sensitivity analyses using PP analysis population may be performed for secondary endpoints, if applicable.

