2.5 Sample Size Determination

No formal sample size calculations based on statistical power were performed. The sample size is determined based upon clinical considerations and the ability to detect a strong clinical efficacy signal.

Proprietary and Confidential Pg. 11 of 38

Up to 15 subjects may be dosed in the study. The actual number of subjects will depend on the criteria for dose escalation.

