3.0 GENERAL ANALYSIS CONSIDERATION

The subjects will be followed in a longitudinal manner, and all relevant information will be collected. The analysis of the data will be descriptive in nature. Descriptive statistics include subject count, mean, median, standard deviation, coefficient of variation, minimum, and maximum for continuous variables and count and percentage for categorical variables. The 95% confidence interval (CI) for the mean and the percentiles may also be included, if appropriate. Safety and efficacy variables will be summarized by dose cohort, and safety and efficacy results related to dose levels will be examined. Data collected in a longitudinal manner may be analyzed using longitudinal methods, such as mixed effect models, which take into account the correlation among the observations taken at various time points within a subject. Subgroup analyses may be performed, if appropriate.

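### The pre/post ABR comparison in SAP 11.2 switches from Poisson to negative binomial regression on an overdispersion test and states no term for the pairing, which widens the interval and costs power for moderate falls

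*SAP*

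**What the plan says.** SAP section 11.2 commits to a regression comparison: "A comparison of pre-infusion and post-infusion ABR using Poisson regression model followed by a test for overdispersion will be performed". It continues: "The ABR will be analyzed using negative binomial regression if overdispersion exists". It names neither the overdispersion test nor its level. It states no subject term, random effect, clustering or robust variance, and does not say whether the comparison is pooled or by cohort.

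The only paired method for ABR is optional: "A comparison using a Wilcoxon signed-rank test may also be performed".

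The same section repeats the ABR analyses for treated bleeds and extends the route further: "The Annualized FVIII use and Annualized FVIII infusion rate will be analyzed similarly as ABR". For one sister endpoint the pairing is explicit and mandatory: "The post-infusion and pre-infusion annualized FVIII use will be compared using a paired t-test".

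Section 3.0 calls the analysis descriptive and adds a general permission: "Data collected in a longitudinal manner may be analyzed using longitudinal methods, such as mixed effect models, which take into account the correlation". It does not tie this to ABR. Section 2.5 states "Up to 15 subjects may be dosed in the study" and "No formal sample size calculations based on statistical power were performed".

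**The concern.** The question is whether the same man's bleeding rate changes after infusion, and each subject supplies one count before and one after. A Poisson model with only a period term assumes that all subjects share one rate within a period. An overdispersion test on that model rejects when subjects differ from one another. Such differences are to be expected: section 2.3 requires at least 12 bleeds in the previous 12 months from on-demand subjects and sets no minimum for subjects on prophylaxis.

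Those level differences largely cancel when a subject is compared with himself. A negative binomial model without a subject term does not cancel them. It puts the between-subject variance into the standard error of the period effect, as if the before and after counts came from two separate groups. A moderate fall in bleeding could then be reported with an interval too wide to show it, although the paired data would. The same holds for treated bleeds and for the FVIII infusion rate.

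**Working it through.** The SAP gives no ABR power, effect size, dispersion or interval, so there is no figure of its own to reproduce.

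**Inputs.** From the SAP: at most 15 subjects (2.5) and the model sequence (11.2). Assumed: mean baseline rate 12 per year; one year before and one year after; a gamma subject effect with variance a = 0.25, 0.5 or 1.0, shared by both periods; two-sided 5% level; rate ratios (RR) 1.0, 0.7, 0.5 and 0.1.

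**Closed form.** Let m0 and m1 be the mean counts per subject before and after.
- Negative binomial, counts taken as independent: SE(log RR) = sqrt{[(1/m0 + a) + (1/m1 + a)]/n}.
- Pairing kept, subject effect shared: SE(log RR) = sqrt{[1/m0 + 1/m1]/n}.

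Take n = 15, m0 = 12, RR 0.5 (so m1 = 6) and a = 0.5:
- 1/12 + 1/6 = 0.25.
- Negative binomial: sqrt[(0.25 + 1.0)/15] = 0.289.
- Paired: sqrt(0.25/15) = 0.129.
- SE ratio: 0.289/0.129 = 2.24. With a t reference on 14 degrees of freedom for the paired interval, the width ratio is 2.24 × 1.960/2.145 = 2.04.

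At RR 0.1, m1 = 1.2 and 1/12 + 1/1.2 = 0.917. The SE ratio is sqrt(1.917/0.917) = 1.45 and the width ratio 1.45 × 1.960/2.145 = 1.32.

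**Simulation** (600 trials per setting; n = 15, baseline 12 per year, shared subject effect only; the paired analysis is a subject-clustered log rate ratio with a t reference):

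| RR | a | Negative binomial rejects | Paired rejects | Width ratio |
|---|---|---|---|---|
| 1.0 | 0.25 / 0.5 / 1.0 | 0.00 / 0.00 / 0.00 | 0.05 / 0.07 / 0.08 | 1.81 / 2.37 / 3.26 |
| 0.7 | 0.25 / 0.5 / 1.0 | 0.36 / 0.11 / 0.02 | 0.83 / 0.84 / 0.81 | 1.68 / 2.28 / 3.07 |
| 0.5 | 0.25 / 0.5 / 1.0 | 0.97 / 0.82 / 0.45 | 1.00 / 1.00 / 1.00 | 1.55 / 2.04 / 2.74 |
| 0.1 | 0.25 / 0.5 / 1.0 | 1.00 / 1.00 / 1.00 | 1.00 / 1.00 / 1.00 | 1.14 / 1.33 / 1.66 |

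The overdispersion test (Pearson chi-square, 5%) fired in 94-100% of these trials, although no within-subject excess variation was present.

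**Population mixed as in section 2.3** (assumed: 4 on-demand subjects at 12-24 per year, 11 on prophylaxis with mean 4 per year; variance of individual change 0 to 0.5). The test fired in 100% of trials. The planned route rejected a true null in 0.0-0.3%. For a 50% fall its power was 24-31%, against 72-91% for Wilcoxon, and its interval was 1.6-2.5 times the clustered one. For a 90% fall both had 100% power and the interval was 1.3-1.5 times as wide.

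**When individual change also varies** (n = 15, baseline 12, a = 0.5, added subject-by-period variance 0.2 / 0.5 / 1.0):
- Width ratio at RR 0.5: 1.35 / 1.13 / 1.02.
- Power at RR 0.5: negative binomial 0.59 / 0.51 / 0.36, paired 0.78 / 0.60 / 0.40.
- Plain Poisson rejects a true null in 0.36 / 0.50 / 0.61 of trials.

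**Limit of the signed-rank test.** With five subjects the smallest two-sided exact p-value is 2/2^5 = 2/32 = 0.0625, so it cannot reach 5%.

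**The case against.** Independence is an inference from silence. Section 11.2 names model families and gives no covariance structure, section 3.0 permits mixed models, and the signed-rank test is allowed. A reader might infer that the SAP prescribes an independence model; it does not say so. What stands is that the mandatory text names only the count models and that both routes to pairing are optional. Two analysts could follow it and report different intervals.

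A reader might also infer that the comparison loses most of its power, or that its interval always doubles. The documents support neither. Section 2.5 looks for a strong efficacy signal, and for a 90% fall nothing is lost in power at n = 15. Over all settings tried the width ratio ran from 0.9 to 4.3, depending on rates and dispersion that the SAP does not give. Doses span 6E12 to 6E13 vg/kg, so subjects may well differ in their change, and the loss then shrinks.

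Nor is ABR the main endpoint here. The primary efficacy endpoints in section 11.1 are both FVIII activity; the remark in 11.2.1 on a primary clinical endpoint describes traditional use for replacement therapy. Individual ABR and change from pre-infusion will be reported whatever the model shows. The harm should not be pictured in a very small lower-dose cohort either: the flow chart in 2.2 shows as few as one to four subjects at a dose, where the signed-rank test cannot reach 5%.

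These points limit the size of the concern. They do not supply a reason to keep the switch.

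**Conclusion.** The point holds in limited form. On the ordinary reading, the planned route moves to the negative binomial model because subjects differ, and that model is inefficient for a paired contrast. With 15 subjects and mainly shared heterogeneity, the interval is about 1.3 to 3 times as wide as a paired one, rejection under the null is near zero, and much of the power is lost for falls of about 30-50%. For a fall near 90% only the width suffers, by about 1.3 to 1.5 times (1.1 to 1.7 over the variances in the table). When individual change varies as much as subject level, the loss largely disappears.

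Baseline rates, dispersion, effect sizes and equal one-year periods are assumptions. The error is conservative, so it creates no false claim of efficacy, and it affects a secondary endpoint in a descriptive analysis with no stated power. Staying with plain Poisson is no remedy: it rejects a true null far too often once change varies between subjects. The change is worth making because a better method costs almost nothing.

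**What to change.** In section 11.2, remove the test-driven switch. For ABR, treated bleeds and FVIII infusion rate, prespecify one paired count model for the pooled pre/post comparison, with period as fixed effect and log(days in period) as offset. Choose one of two forms in advance:
- a subject random intercept with a dispersion term; or
- GEE clustered on subject, with small-sample-corrected variance and a t reference.

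Make the Wilcoxon signed-rank test mandatory as an accompanying test for the pooled comparison only. For cohorts too small to fit the model or to reach 5% with Wilcoxon (five or fewer subjects), report individual and descriptive within-subject changes without a test.

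The cost is SAP wording and a few lines of code, with no new data. Two downsides should be acknowledged. The random-intercept model may not converge with sparse counts. Robust variance is slightly liberal at small n: the clustered analysis rejected a true null in 5-8% of trials at n = 15 and baseline 12, and in 10-11% at n = 7 when individual change also varied.
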